7.2. Number of Subjects

Approximately 40 subjects will be enrolled in the study assuming about a 40% drop out rate to achieve 12 subjects who complete each part of the study for a total of 24 completed subjects. Subjects will complete either Part 1 or Part 2, but not both.

Subjects who require a tazemetostat dose interruption or reduction during Cycle 1 of either Part 1 or Part 2 will be replaced. During Cycle 1, subjects who miss two or more consecutive tazemetostat/itraconazole/rifampin doses or more than three tazemetostat/itraconazole/rifampin doses in total will be replaced. Subjects who miss two or more consecutive PK blood sample collections during either part of Cycle 1 will be replaced. Subjects that require replacement will be discontinued from study treatment.

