7.3. Treatment Assignment

After obtaining written, informed consent, subjects with advanced malignancies will be screened according to the exclusion and inclusion criteria. Subjects who have complied with all selection criteria will receive a unique subject number upon enrollment in the study. Subject numbers will be allocated sequentially in the order in which subjects are enrolled. The Investigator or designee will enter the corresponding subject number and complete each eCRF.

Subjects will be assigned to the study as follows:

Part 1: Tazemetostat and Itraconazole Drug Interaction ([Figure 2](#))

Part 2: Tazemetostat and Rifampin Drug Interaction ([Figure 3](#))

Part 1: Tazemetostat and Itraconazole Drug Interaction

Subjects in Part 1 of the study will receive a single oral, 400 mg dose of tazemetostat on Day 1, 15, and Day 36. The subjects will receive tazemetostat (oral 400 mg dose) tablets to be taken twice daily from Day 3 – 14 and Day 21 – 35. In addition, the subjects will receive oral 200 mg itraconazole once daily from Day 18 – 38. Detailed schedule of assessments is provided in [Table 3](#).

Note: Subjects will not be dosed with tazemetostat on day 2, from day 16 – 20, 37, and 38.

Part 2: Tazemetostat and Rifampin Drug Interaction

Subjects in Part 2 of the study will receive a single, oral, 800 mg dose of tazemetostat on Day 1, 15 and Day 24. The subjects will receive tazemetostat (oral 800 mg dose) tablets to be taken twice daily from Day 3 – 14 and Day 17 – 23. In addition, the subjects will receive oral 600 mg rifampin once daily from Day 17 – 25. Detailed schedule of assessments is provided in [Table 4](#).

Note: Subjects will not be dosed with tazemetostat on day 2, 16, and 25.

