13. STATISTICS

Summaries of continuous variables will present the number of subjects included in the analysis (N), the mean and standard deviation (SD), the median, the minimum, and the maximum statistics. Counts and percentages will be presented in summaries of categorical variables. The denominator for each percentage will be the number of subjects in the population unless otherwise specified. In general, missing data will not be imputed unless otherwise specified.

All disposition, baseline demographics and disease characteristics will be descriptively summarized for the Safety population

Analyses will be done separately for each study part and overall.

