5. ANALYSIS POPULATIONS

The agreement and approval of subjects to be included/excluded from each analysis population will be established prior to database lock. The population definitions are as follows:

- **Enrolled population** will include all subjects who signed informed consent and met all screening criteria. The Enrolled population will be used for summaries of demographic and baseline disease characteristic.
- **Safety population** will consist of all subjects in the Enrolled population who receive at least one dose or partial dose of study drugs and have at least one post-dose safety observation recorded. The Safety population will be used for summaries and analyses of the safety and tolerability.
- **Pharmacokinetic (PK) population** will include all subjects in the Safety population who have at least one post-dose sample collected to allow estimation of the PK parameters. The PK population will be used for PK data analysis.

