6.3. UNIT CONVENTIONS

- 1 year = 365.25 days. Year is calculated as (days/365.25) and will be rounded to 1 digit after the decimal point (tenths) for presentation purposes.
- 1 month = 30.4375 days. Month is calculated as (days/30.4375) and will be rounded to 1 digit after the decimal point (tenths) for presentation purposes.
- 1 pound = 0.454 kg and 1 kg = 2.2 pounds.
- 1 inch = 2.54 cm and 1 cm = 0.3937 inches.
- Body mass index (BMI) calculated as [weight (kg)/height (m)²]
- BMI calculated as [weight (lb) / height (in)²] x 703
- Unless otherwise specified, percentages will be calculated based on the number of subjects specified by the appropriate analysis population definition.
- All tables, listings, figures will be produced in landscape orientation using the default Courier New 9-point font whenever feasible. Output files will be created in rich text file (RTF) format.

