1) For Cycle 1 (Days 1-26):

- Average dose intensity (mg BID/day) = total amount of tazemetostat taken (mg) / (2* 22) (days) (mg BID/day)
- Planned average dose intensity (mg BID/day) = $[800*3+800*2*(12+7)]/(2*22) = 32,800/(2*22) = 745.45$ (mg BID/day)

2) For Cycle 2+ onwards

Average dose intensity (mg BID/day) = total amount of tazemetostat taken (mg) / [2 * duration of exposure (days)] (mg BID/day)
 where duration of exposure (days) = [(date of last actual dose of tazemetostat – date of first dose of tazemetostat) + 1] (days)

- For assessment of tolerability, numbers of subjects requiring dose reductions, treatment interruption or treatment discontinuation in response to AEs (based on action taken for reported AEs)

The following summaries of study drugs itraconazole in part 1 and rifampin in part 2 will be presented.

Study Part 1:

- Summary statistics for the total amount of itraconazole received (mg)
- Number (%) of subjects who received <4200 mg, 4200 mg and > 4200 mg of itraconazole

Study Part 2:

- Summary statistics for the total amount of rifampin received (mg)
- Number (%) of subjects who received < 5400 mg, 5400 mg and > 5400 mg of rifampin

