16. SAFETY OUTCOMES AND ANALYSIS

All safety summaries will be based on the Safety population.

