16.1. ADVERSE EVENTS

AEs will be coded using MedDRA v23.1. Summary tables will be based on treatment emergent adverse events (TEAEs) which are defined as AEs that started or worsened in severity on or after the day of the first dose of study drug through 30 days after the end of study drug or the initiation of subsequent anticancer therapy, whichever is earlier. All AEs, treatment emergent or otherwise, will be presented in AE listings.

Each summary table will include the incidence (number and percentage) of subjects reporting any TEAE, as well as, by SOC and PT. A subject will be counted only once with an SOC, even if the subject experienced more than one TEAEs within that specific SOC (likewise for PT).

Investigator assessed severity grade will be based on the National Cancer Institute CTCAE v5.0. A subject will be counted only once with the worst severity grade within a SOC and/or PT.

Investigator assessed causality to study drug will be categorized as “not related,” “unlikely related,” “possibly related,” or “probably related” to study drug. For summary purposes, treatment-related TEAEs will include events with relationship to study drug classified as “not related” including both “not related” and “unlikely related” or “related” involving both “possibly related” and “probably related”. A TEAE with a missing causality will be classified as “related” to study drug. A subject will be counted only once at the strongest causality within a SOC and/or PT (related over not related).

TEAEs of special interest are defined in Section 12.4.2 of the protocol.

In accordance with the TEAE table presentation described above, AEs will be summarized as follows:

- TEAEs
- TEAEs of grade 3 or 4
- Treatment-related TEAEs
- Treatment-related TEAEs of grade 3 or 4
- TEAEs leading to dose interruption
- TEAEs leading to dose reduction
- TEAEs leading to discontinuation of study drug
- Serious adverse events (SAEs)
- Treatment-related SAEs

-
- TEAEs leading to death
 - TEAEs of special interest

For treatment-related summaries, relationship will be summarized by each study drug (Part 1: tazemetostat or itraconazole; Part 2: tazemetostat or rifampin).

Separate listings of SAEs, TEAEs leading to discontinuation of study drug, TEAEs leading to dose modifications, and TEAEs with an outcome of death will be provided. A listing of TEAEs of special interest will also be provided.

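### SAP 16.1 divides itraconazole- and rifampin-related event counts by all Safety subjects in the part, including any who left before that drug started

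*SAP*

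**What the plan says.** SAP 16 sets the population for every safety table: "All safety summaries will be based on the Safety population". SAP 5 admits to that population enrolled subjects "who receive at least one dose or partial dose of study drugs and have at least one post-dose safety observation recorded". Receipt of itraconazole or rifampin is not required, and neither of the other two populations defined there (Enrolled, PK) requires it.

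SAP 6.3 gives the default denominator: "percentages will be calculated based on the number of subjects specified by the appropriate analysis population definition". Protocol 13 agrees: "The denominator for each percentage will be the number of subjects in the population unless otherwise specified". Both allow exceptions if specified. SAP 16.1 specifies none where it introduces the drug-specific summaries: "For treatment-related summaries, relationship will be summarized by each study drug (Part 1: tazemetostat or itraconazole; Part 2: tazemetostat or rifampin"). SAP 6.1 presents results by study part and overall.

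On timing, SAP 6.2.1 has both parts start on Day 1 with tazemetostat. In Part 1, Protocol 7.3 says "the subjects will receive oral 200 mg itraconazole once daily from Day 18"; in Part 2 the same section starts rifampin on Day 17. Protocol 7.2 plans enrolment "assuming about a 40% drop out rate", and Protocol 7.5.1 takes off treatment any subject who needs a tazemetostat interruption or reduction in Cycle 1.

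SAP 14 summarises exposure in the Safety population. For Part 1, SAP 14.1 lists "Number (%) of subjects who received <4200 mg, 4200 mg and > 4200 mg of itraconazole", with matching rifampin categories around 5400 mg.

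**The concern.** A subject who leaves while still on tazemetostat alone cannot have an event caused by the second drug, yet is counted as at risk of one. The percentage labelled itraconazole- or rifampin-related then depends partly on how many subjects left in the first two and a half weeks. Tazemetostat-related percentages do not have this problem, because every subject has taken tazemetostat from Day 1.

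The exposure table has a related weakness. Its lowest category holds both subjects who started the second drug and missed doses and subjects who never started it. These are different facts about the conduct of the study, and the table does not yield the number exposed.

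**Working it through.** **Inputs.** About 40 enrolled, 40% dropout, 12 completers per part (Protocol 7.2, SAP 4.2). Cycle 1 ends on Day 39 in Part 1 and Day 26 in Part 2. The second drug starts on Day 18 and Day 17 respectively (Protocol 7.3). The documents do not say how many subjects are expected to leave before those days; call this x per part.

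**The plan's own figures.** 24/(1-0.40) = 40, as stated. Per part, 12/0.60 = 20, so 20-12 = 8 dropouts. Full planned dosing is (38-18+1) × 200 = 4200 mg of itraconazole and (25-17+1) × 600 = 5400 mg of rifampin, which match the category limits in SAP 14.1.

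**Assumption.** All 20 per part are dosed and enter the Safety population. The documents give enrolment only as an approximate total.

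**Effect of the denominator.** With k affected subjects, the plan reports k/20, while the rate among exposed subjects is k/(20-x). The ratio of the first to the second is (20-x)/20. For k = 3:

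| x | Exposed N | Plan reports | Among exposed | Ratio |
|---|---|---|---|---|
| 0 | 20 | 15.0% | 15.0% | 1.00 |
| 2 | 18 | 15.0% | 16.7% | 0.90 |
| 4 | 16 | 15.0% | 18.8% | 0.80 |
| 6 | 14 | 15.0% | 21.4% | 0.70 |
| 8 | 12 | 15.0% | 25.0% | 0.60 |

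**A middle case.** If the 8 dropouts are spread evenly over Cycle 1 (an assumption):

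- Part 1: x = 8 × 17/39 = 3.5; ratio (20-3.5)/20 = 0.83.
- Part 2: x = 8 × 16/26 = 4.9; ratio (20-4.9)/20 = 0.75.

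A constant dropout hazard gives x of about 4.0 and 5.4, hence ratios of 0.80 and 0.73.

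**What can act the other way.** Under SAP 16.1 the treatment-emergent window opens at the first dose of study drug, which is tazemetostat on Day 1, and a missing causality is classed as related. An event before Day 18 with no itraconazole causality entry can therefore enter the itraconazole-related numerator. Take x = 4 and three exposed subjects with genuine events. One such extra subject makes the reported figure 4/20 = 20%, above the 3/16 = 18.75% among exposed subjects. A missing entry is plausible, since Protocol 12.5 words the causality question around tazemetostat alone.

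**The case against.** The strongest reply is that the direction is not fixed and little is hidden. The missing-causality rule can inflate the numerator, as shown above. Counts appear beside percentages, exposure is listed by subject, and SAP 9 summarises discontinuations and replacements with reasons, so the exposed N can be reconstructed. No decision rule uses these percentages, and the exact 95% interval for 3/20 is about 3% to 38%, wide beside a move from 15% to 19%. The secondary objective concerns the safety of tazemetostat when co-administered, not the rate of events attributed to the second drug.

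Most of this stands, and it limits the point to descriptive percentages. It does not remove it. The denominator is a stated rule rather than a gap, and having to rebuild the exposed N from listings is a reason to print it.

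Three stronger readings are tempting but unsupported:

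- A reader might infer that the rates must be too low, by an amount set only by early dropout. With no early leavers there is no dilution, and the missing-causality rule can work against it.
- A reader might take 0.60 as the expected factor. It needs all eight dropouts to leave before the second drug starts, which nothing in the documents suggests.
- A reader might conclude that never-started subjects add zeros to the mean amount of itraconazole or rifampin. The SAP does not say so. Missing data stay missing (6.2.5) and continuous summaries count non-missing values (7), so it is open whether such subjects enter as 0 or as missing.

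**Conclusion.** The point holds as a conditional dilution. As written, the plan divides events attributed to the second drug by subjects who may never have taken it. On 20 dosed subjects per part, the denominator alone multiplies the rate among exposed subjects by a factor between 1.00 and 0.60, with about 0.8 (Part 1) and 0.75 (Part 2) under evenly spread dropout. The number of early leavers and their timing are assumptions. The net direction also depends on how many events before the second drug lack a causality entry.

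The merging of never-started with partially dosed subjects below 4200 mg and 5400 mg follows from the categories themselves and needs no assumption beyond at least one early leaver. PK endpoints and power are unaffected. The change should be made because the design makes early exit likely and the remedy is small.

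**What to change.** In SAP 16.1, state that for itraconazole-related and rifampin-related TEAE and SAE summaries:

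- the denominator is the Safety subjects in that part with at least one dose of that drug;
- only events with onset or worsening on or after the first dose of that drug are counted;
- that N appears in the column header.

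The onset rule is needed along with the denominator. Without it, a subject who left before the second drug with a missing causality could be in the numerator but not in the denominator.

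In SAP 14.1, summarise itraconazole and rifampin exposure in the same subsets, or show 0 mg as its own category and say whether never-started subjects enter the mean as 0 or are left out. Keep the full Safety population for tazemetostat-related summaries.

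The cost is a few sentences in the SAP and one extra N in the table shells, settled before database lock. No new data are needed.

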10.5.1. Missed Doses

Tazemetostat doses must be taken 12 hours apart at approximately the same time each day, for example between 7 – 9 am for the morning dose and 7 – 9 pm for the evening dose. If a dose of any study drug (tazemetostat, itraconazole or rifampin) is missed, then that drug should be administered at the next dosing time point.

Vomiting: If the subject vomits after study drug administration, then that study drug (tazemetostat, itraconazole or rifampin) should be administered at the next dosing time point. All doses given, missed, and vomited, should be recorded.

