12.5. Relationship to Study Drug

A qualified Investigator must make the determination of relationship to study drug for each AE. The Investigator should decide whether, in his or her medical judgment there is a reasonable possibility that the event may have been caused by tazemetostat.

The following should be considered when assessing the relationship of an AE to study treatment:

- Temporal relationship of the onset of the event to the first dose of study drug
- The course of the event, considering especially the effect of discontinuation of study treatment or the reintroduction of study treatment, as applicable
- Whether the event is known to be associated with the study treatment or with other similar treatments
- The presence of risk factors in the study subject known to increase the occurrence of the event
- The presence of non-study treatment-related factors that are known to be associated with the occurrence of the event.

Investigators must also systematically assess the causal relationship of AEs to the study drug using the following definitions (the decisive factor being the temporal relationship between the AE and administration of the study drug):

- **Probable:** A causal relationship is clinically/biologically highly plausible, there is a plausible time sequence between onset of the AE and administration of the study drug, and there is a reasonable response on withdrawal.
- **Possible:** A causal relationship is clinically/biologically plausible and there is a plausible time sequence between onset of the AE and administration of the study drug.
- **Unlikely:** A causal relationship is improbable, and another documented cause of the AE is most plausible.
- **Unrelated:** A causal relationship can be definitively excluded, and another documented cause of the AE is most plausible.

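### SAP 16.1 tabulates relatedness to itraconazole and rifampin and counts missing causality as related, without requiring that the drug had been given; protocol 12.5 does not clearly collect per-drug causality

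*SAP*

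**What the plan says.** **SAP 16.1 (Adverse Events).** For the treatment-related summaries, "relationship will be summarized by each study drug", and the drugs are named for each part: tazemetostat or itraconazole in Part 1, tazemetostat or rifampin in Part 2. The same section groups the causality categories into related and not related. It adds that "A TEAE with a missing causality will be classified as" related to study drug. No condition refers to which drug was rated, or to whether that drug had been started when the event began. SAP 7 confirms that this is a deliberate imputation: it lists missing relationship as an exception to the general rule that missing safety data are not imputed.

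TEAEs are "AEs that started or worsened in severity on or after the day of the first dose of study drug". SAP 6.2.1 sets the reference date for safety measures as the first dose of any study drug, which is tazemetostat on Day 1 in both parts.

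**Protocol 12.5 (Relationship to Study Drug).** The investigator decides whether "there is a reasonable possibility that the event may have been caused by tazemetostat". The rating instruction follows: "Investigators must also systematically assess the causal relationship of AEs to the study drug using the following definitions". One four-level scale is given. Nothing in the section asks for a separate rating for itraconazole or rifampin.

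**Use of the term elsewhere.** Protocol 10.5.1 uses it broadly: "If a dose of any study drug (tazemetostat, itraconazole or rifampin) is missed". Section 10.6 does the same. The synopsis, Table 6 and Section 10.1 reserve the label for tazemetostat.

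**The concern.** The analysis plan promises output at a finer level than the protocol's causality question. A single rating against one study drug cannot be split into two per-drug tables. If no per-drug rating exists, the SAP's only instruction for an absent causality is to call it related.

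The second difficulty remains even if per-drug ratings are collected. The design is a fixed sequence in which the second drug starts about two and a half weeks into Cycle 1, while the TEAE window opens on Day 1. A site may reasonably leave the itraconazole or rifampin field blank for an event that began before that drug was given. The rule turns that blank into a related event.

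Counting missing as related is a sound, cautious default for a drug the subject took and the investigator was asked about. For a drug not yet taken it records an attribution that cannot be true. At stake is whether the rows for itraconazole and rifampin in the treatment-related TEAE and SAE tables can be taken at face value.

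**Working it through.** The plan states no figure for this point, so there is none to reproduce. The check is a comparison of the two texts, a count of days, and an illustration of what blanks would do.

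**1. Data needed against data requested**

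- Needed by SAP 16.1: two relatedness values per TEAE (tazemetostat, and itraconazole or rifampin).
- Requested by protocol 12.5: one value, under a question that names tazemetostat.
- Possible other source: the eCRF, which SAP 1 says should be read with the plan but which is not among the documents.

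Three cases follow:

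- (a) No per-drug field, and the missing rule applied drug by drug: every TEAE becomes related to itraconazole or rifampin.
- (b) No per-drug field, and the rule applied once per event: the itraconazole and rifampin tables have no data of their own.
- (c) Per-drug fields exist: only blank fields are affected.

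**2. Dosing days, checked against SAP 14.1**

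- Itraconazole, Days 18 to 38: 38 − 18 + 1 = 21 doses; 21 × 200 mg = 4200 mg.
- Rifampin, Days 17 to 25: 25 − 17 + 1 = 9 doses; 9 × 600 mg = 5400 mg.

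Both totals match the category cut-offs in SAP 14.1, so the start days are Day 18 and Day 17.

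**3. Part of Cycle 1 before the second drug**

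- Part 1: Days 1 to 17 of 39; 17/39 = 43.6%.
- Part 2: Days 1 to 16 of 26; 16/26 = 61.5%.

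These are shares of calendar days, not of events.

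**4. Subjects who never reach the second drug**

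The Safety population (SAP 5) requires one full or partial dose of study drugs and one post-dose safety observation, so a subject who received only tazemetostat is included. The planning assumption of about 40% drop-out among about 40 subjects is 0.40 × 40 = 16. The documents do not say when drop-outs are expected, so on that assumption the number leaving before Day 18 or Day 17 could lie anywhere from 0 to 16.

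**5. Effect of blanks in case (c)**

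No blank rate is given. Assume that a share m of causality fields is blank, independently across events, and that a subject has k TEAEs starting before the second drug. The chance of at least one false related event is 1 − (1 − m)^k. Example: 1 − 0.95^5 = 22.6%.

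| Assumed blank rate m | k = 3 | k = 5 | k = 10 |
|---|---|---|---|
| 0% | 0% | 0% | 0% |
| 1% | 3.0% | 4.9% | 9.6% |
| 5% | 14.3% | 22.6% | 40.1% |
| 10% | 27.1% | 41.0% | 65.1% |

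Both m and k are assumptions. With complete fields the effect is zero.

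**The case against.** **The term is ambiguous.** Only the opening question in protocol 12.5 names tazemetostat. The rating instruction says study drug, and 10.5.1 and 10.6 count all three agents as study drugs. This stands as far as it goes: a reader might infer that the protocol rules out any assessment of itraconazole or rifampin, and the text does not prove that. But on the broad reading there is still only one rating, and it cannot be divided by drug.

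**The eCRF probably has the fields.** SAP 16.1 names the drugs for each part, which suggests that per-drug fields were expected. That is a fair inference, and it makes the data-availability part conditional. It does not answer the exposure part, unless the eCRF also has a not-applicable value or an onset check.

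**The missing rule may be meant per event.** It speaks of a TEAE with a missing causality, and an event with a completed tazemetostat rating does not plainly qualify. The SAP does not say how the rule works once relatedness is split by drug. This is a good reason to write the rule out, since both readings are open to the programmer.

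**The consequences are limited.** This stands in full. The secondary safety endpoints are AE assessment, examinations, vital signs, ECG, laboratory tests, ECOG status and concomitant medication. The all-causality TEAE, grade 3 or 4, SAE, discontinuation, death and special-interest tables do not use causality, and every AE is listed. A reader might infer that the co-administration safety objective could not be assessed; the documents do not support that.

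**Conclusion.** The point holds in a limited form. SAP 16.1 contains a stated rule that, read literally, can label an event as related to itraconazole or rifampin in a subject who had not taken it. Protocol 12.5 does not by itself supply the per-drug ratings that the tables need. The first statement rests on the SAP text and the dosing days; the second is conditional on the unseen eCRF.

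The size is unknown and may be small. It is zero if causality fields are complete and per-drug. It reaches all TEAEs only if no per-drug field exists and the rule is applied drug by drug.

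Two stronger readings should be resisted:

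- One might apply the pooled TEAE rate in protocol 5.5.1 (857/895, 96%) to 40 subjects and expect 857/895 × 40 = 38.3, about 38 subjects with a falsely related event. That is a worst case under (a), using an adult and pediatric monotherapy database rather than a rate for 39- or 26-day cycles.
- One might read 43.6% and 61.5% as shares of misattributed events. They show how long the exposure gap lasts. Misattribution also needs a blank field.

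The effect is confined to the descriptive per-drug relatedness tables for TEAEs and SAEs. All-causality tables, listings and PK results are unaffected. The correction is still worth making before database lock, because the rule produces an impossible attribution and is easy to limit.

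**What to change.** 1. **SAP 16.1.** State that the missing rule is applied separately for each drug, and that missing is set to related only for a drug with at least one dose on or before the AE onset date. Otherwise record not applicable and count the event as not related to that drug. This sets only the start of attribution. If the sponsor does not want blanks imputed long after itraconazole or rifampin has stopped (for example in Cycle 2 and beyond), an end limit should be stated as well.
2. **Protocol 12.5 and eCRF.** Ask for causality to each study drug by name, with a not-applicable option.
3. **If per-drug causality was not collected.** Drop the itraconazole and rifampin relatedness tables and report relatedness as it was asked.

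**Cost.** Item 1 takes a sentence or two and minor programming. Item 2 is light if the fields already exist. If they do not, new protocol wording will not recover ratings already missed, so the choice is between data queries and losing those tables.
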